### **11.2 Analysis of Adverse Events**

Analyses of adverse events will include only "treatment-emergent" events (TEAE), i.e., those that have an onset (worst CTC grade) prior to or on the 30 days of last dose of study drug in combination period. TEAEs will be coded and summarized by preferred term according to the Medical Dictionary for Regulatory Activities (MedDRA) adverse event coding dictionary. Subjects reporting more than one AE will be counted only once in the overall analysis. Summary data by each treatment arm will be presented by but not limited to the following statistics:

- The numbers and percentage of subjects experiencing any TEAE;
- The numbers and percentage of subjects experiencing grade 3 or 4 TEAEs;
- The numbers and percentage of subjects experiencing TEAEs that investigator found having a reasonable possibility related to veliparib/placebo;
- The numbers and percentage of subjects experiencing grade 3 or 4 TEAEs that investigator found having a reasonable possibility related to veliparib/placebo;
- The numbers and percentage of subjects experiencing TEAEs that led to study discontinuation due to disease progression or not due to disease progression;
- The numbers and percentage of subjects experiencing TEAEs that led to veliparib/placebo/carboplatin/etoposide discontinuation due to disease progression or not due to disease progression;
- The numbers and percentage of subjects experiencing TEAEs that led to veliparib/placebo/carboplatin/etoposide reduction, interruption, or delay. If an AE led to more than one actions, consider them as one;
- The numbers and percentage of subjects experiencing any serious TEAE;
- The numbers and percentage of subjects experiencing any serious TEAE that investigator found having a reasonable possibility related to veliparib/placebo;
- The numbers and percentage of subjects experiencing any TEAE of special interest;
- The numbers and percentage of subjects experiencing any grade 3 or 4 TEAE of special interest;
- Listing of TEAEs that led to death;
- The numbers and percentage of subjects experiencing TEAEs that led to death;
- The numbers and percentage of subjects experiencing TEAEs that led to death that investigator found having a reasonable possibility related to veliparib/placebo;

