#### **6.4 Relationship to Study Drug**

The investigator will use the following definitions to assess the relationship of the adverse event to the use of study drug:

Reasonable Possibility	After consideration of factors including timing of the event, biologic plausibility, clinical judgment, and potential alternative causes, there is sufficient evidence (information to suggest a causal relationship).
No Reasonable Possibility	After consideration of factors including timing of the event, biologic plausibility, clinical judgment and potential alternative causes there is insufficient evidence (information to suggest a causal relationship).

For causality assessments, events assessed as having a reasonable possibility of being related to the study drug will be considered "associated." Events assessed as having no reasonable possibility of being related to study drug will be considered "not associated." In addition, when the investigator has not reported a causality or deemed it not assessable, AbbVie will consider the event associated. For the purposes of this study, causality assessments will be attributed to veliparib/placebo or carboplatin or etoposide separately.

If an investigator's opinion of no reasonable possibility of being related to study drug is given, another cause of event must be provided by the investigator for the serious adverse event.

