## **6.5 Adverse Event Collection Period**

[figure not shown]
All protocol related serious adverse events and nonserious adverse events must be collected from the signing of the study specific informed consent until study drug administration.

In addition, all adverse events reported from the time of study drug administration until 30 days following discontinuation of study drug administration have elapsed will be collected, whether solicited or spontaneously reported by the subject.

Serious and nonserious adverse events occurring after the study specific informed consent is signed but prior to the initial dose of study drugs will be collected only if they are considered by the Investigator to be causally related to the study-required procedures.

Adverse event information will be collected as shown in [Figure 4](#).

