#### **8.1.7.2 Adverse Events**

Analyses of adverse events will include only "treatment-emergent" events, i.e., those that have an onset on or after the day of the first dose of study drug (veliparib or placebo). Analyses will not include those that have an onset greater than 30 days after the last dose of study drug.

Treatment-emergent adverse events will be coded and summarized by system organ class and preferred term according to the Medical Dictionary for Regulatory Activities (MedDRA) adverse event coding dictionary. The percentage of subjects experiencing an adverse event at a given NCI CTCAE version 4.0 grade, and relationship to study drug will be provided. For Phase 1, all summaries will be done by dose level. For Phase 2, comparisons of the percentages of subjects experiencing an adverse event between Arm A and Arm C as well as between Arm B and Arm C will be performed using Fisher's exact test.

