### **Definition of Study Drug**

Unless otherwise specified, the study drug in this document refers to veliparib/placebo, and carboplatin/etoposide. The first dose date of study drug for combination period is defined as the date of the 1st dose of veliparib/placebo or carboplatin/etoposide received during combination period, whichever occurs first. The last dose date of study drug for combination period is defined as the date of the last dose of veliparib/placebo or carboplatin/etoposide received during combination period, whichever occurs later. The first dose date of study drug for maintenance period is defined as the date of the 1st dose of veliparib/placebo received during maintenance period. The last dose date of study drug for maintenance period is defined as the date of the last dose of veliparib/placebo received during maintenance period.

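### SAP 11.2 gives treatment-emergent AEs no start date, does not carry over the protocol rule for unassessed causality, and lists no row for Grade 3 or higher

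*SAP*

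**What the plan says.** **Time window.** SAP 11.2 restricts AE analyses to treatment-emergent events, defined as "those that have an onset (worst CTC grade) prior to or on the 30 days of last dose of study drug in combination period". Protocol 8.1.7.2 sets two limits. The lower one is "those that have an onset on or after the day of the first dose of study drug (veliparib or placebo"; the upper one is "Analyses will not include those that have an onset greater than 30 days after the last dose of study drug". Some events before dosing do reach the database: under Protocol 6.5, AEs between consent and the first dose "will be collected only if they are considered by the Investigator to be causally related to the study-required procedures".

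**Causality.** Four rows in SAP 11.2 (any TEAE, Grade 3 or 4, serious, fatal) count events for which the investigator found a reasonable possibility of a relationship to veliparib/placebo. Protocol 6.4 adds a convention for the remaining cases: "when the investigator has not reported a causality or deemed it not assessable, AbbVie will consider the event associated". SAP 11.2 does not mention it.

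**Severity.** SAP 11.2 lists "The numbers and percentage of subjects experiencing grade 3 or 4 TEAEs", with matching rows for related events and for events of special interest. Fatal events have a listing, a row for "The numbers and percentage of subjects experiencing TEAEs that led to death", and a related version of that row. SAP 11.3 also summarizes deaths by time window and cause. The list in 11.2 is expressly open-ended.

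**The concern.** Safety of the combination is a secondary objective (Protocol 4.0, SAP 4.1), and the TEAE definition feeds every AE table. A rule without a start date counts events that cannot be due to treatment. A related-event rule without a provision for unassessed causality can drop events that the protocol tells the sponsor to treat as associated. A severity row that ends at Grade 4 does not answer the usual question of how many subjects had an event of Grade 3 or worse. The events missing from that row also matter for toxicity: Protocol 6.1.2 keeps deaths attributed solely to progression off the AE form, so the Grade 5 AEs are the other on-study deaths.

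**Working it through.** The plan gives no figure to reproduce here. The check sets the texts side by side and adds simple arithmetic for scale.

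**1. Start date.** Take an AE caused by a screening procedure, with onset after consent and before the first dose.
- Protocol 6.5: collected, because it is procedure-related.
- Protocol 8.1.7.2: excluded, because onset precedes the first dose of veliparib or placebo.
- SAP 11.2: included, because onset is earlier than 30 days after the last combination-period dose, and that is the only test.

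Two other SAP passages might supply the missing limit. SAP 11.1 confines safety summaries to the combination period. SAP 6.0 states: "The first dose date of study drug for combination period is defined as the date of the" first dose of veliparib/placebo or of chemotherapy, whichever is earlier. Neither is applied to AE onset in 11.2. The SAP 6.0 anchor is also not quite the protocol's, which is veliparib/placebo alone. The two dates normally coincide, because veliparib/placebo starts on Day -2 and chemotherapy on Day 1. (The SAP's upper limit also differs from the protocol's, being tied to the combination period. That is a separate matter and is not needed for this point.)

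**2. Causality.** The record can be in one of three states:
- Reasonable possibility: related under both documents.
- No reasonable possibility: not related under both.
- Missing or not assessable: associated under Protocol 6.4, but not an event that the investigator found possibly related, so outside the SAP rows if they are programmed literally.

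Only the third state differs.

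**3. Severity.** Let *a* be the subjects in the Grade 3 or 4 row, *f* those in the fatal row (taken as Grade 5), and *b* those in both. Then

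subjects with Grade 3 or higher = *a* + *f* - *b*.

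No listed row reports *b*, so the total can lie anywhere from the larger of *a* and *f* up to *a* + *f*. With *f* = 3 (assumed) and *a* of at least 3, the rate is uncertain by up to 3/60 = 5.0 points. For events of special interest there is no fatal row, so *f* itself is not tabulated.

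**4. Scale.** SAP 4.3 plans 60 subjects per arm. The number affected is assumed, because the documents do not give it:
- 1 subject: 1/60 = 1.7 points
- 3 subjects: 3/60 = 5.0 points
- 6 subjects: 6/60 = 10.0 points

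The safety tables use the as-treated population, so actual denominators may differ slightly from 60.

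**The case against.** **Start date.** The label itself implies onset after treatment starts, and a programmer would probably read SAP 11.1 and 6.0 that way. Only procedure-related events are collected before dosing, and because they precede treatment they should add noise rather than a difference between arms. This limits the effect, but it does not put the missing limit into the definition.

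**Causality.** A reader might infer that the SAP counts unassessed causality as unrelated. It does not say so; it is silent. The SAP presents itself as elaborating the protocol's methods, nothing in it revokes Protocol 6.4, and Protocol 6.0 asks the investigator to record the relationship for every AE. The gap is therefore an omitted rule. It still matters, because the wording of the rows, followed literally, gives a different count from the protocol's.

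**Severity.** A reader might infer that fatal events are left out or hidden. They are not. They have their own listing, count and related count, they meet the serious-event criteria, and SAP 11.3 covers deaths. Protocol 6.3 itself separates severe (Grade 3/4) from death (Grade 5), and Protocol 8.1.7.2 asks for percentages at a given grade without prescribing a pooled Grade 3 to 5 table. Protocol 6.3 also requires a new AE record when severity increases, so a fatal event first recorded at Grade 3 or 4 would normally have its own record at that grade, unless a worst-grade rule collapses the two. What stands is that Grade 3 or higher incidence is not among the listed rows and cannot be rebuilt from overlapping ones. The open-ended list permits such a table but does not specify it.

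**Direction.** It is tempting to say that these rules make the more toxic arm look safer. The documents do not show that. Investigators are blinded (Protocol 5.5.6), and nothing suggests that missing causality or pre-dose events would cluster in one arm.

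**Conclusion.** The point holds in limited form. The missing start date is a plain departure from Protocol 8.1.7.2: followed as written, the SAP rule counts pre-dose events as treatment-emergent. The causality wording omits a protocol rule and, programmed literally, would undercount related events. The severity rows leave a reporting gap; they do not conceal fatal events. SAP 4.1 explains its deliberate change to the response-rate period, whereas 11.2 explains none of these differences, so they read as drafting gaps.

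The size is probably small: 1.7 points per affected subject, on the planned 60 per arm. Whether any reported count changes depends on such events occurring, and the documents give no frequencies. Within an arm, the first gap can only raise TEAE counts and the second can only lower related counts. No bias between arms is established.

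**What to change.** In SAP 11.2:
1. Add to the TEAE definition that onset must be on or after the day of the first dose of veliparib/placebo. The date exists for everyone in the safety tables, because SAP 5.1 requires at least one such dose for the as-treated population.
2. State that events with missing or not-assessable causality are counted as related, citing Protocol 6.4, in all four related-event rows.
3. Keep the fatal-event rows and add rows for Grade 3 or higher (3, 4 or 5): overall, related, and for events of special interest. Count each subject once.

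The cost is a few phrases and the matching programming flags. No new data are needed.

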**Table 6. Treatment Schematic for Combination Cycles in Phase 2**

Days	-2	-1	1	2	3	4 – 12
Veliparib/Placebo	240 mg BID					
Carboplatin			Once			
Etoposide			Once	Once	Once	

Notes: Starting at Maintenance Day 1 veliparib will be dosed at 400 mg BID monotherapy continuous dosing for 21 days per cycle.

A minimum of 4 cycles of combination treatment are to be administered. If subject/disease status at the completion of Cycle 4 warrants continued combination treatment, up to 2 additional combination cycles (e.g., up to a total of 6) may be administered at investigators discretion.

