### 5.2.3.2 Concomitant Therapy

The locally approved product label, institutional guidelines, local practice, or applicable Summary of Product Characterizations (SmPC) for carboplatin and etoposide should be referenced for any concomitant therapy guidelines.

- Premedication: The prophylactic antiemetics, including 5-HT3 antagonists, according to institution, National Comprehensive Cancer Network (NCCN), European Society for Medical Oncology (ESMO) or American Society of Clinical Oncology (ASCO) guidelines should be given, prior to administration of carboplatin and etoposide. Prophylaxis with anti-emetics (e.g., 5-HT3 antagonists such as ondansetron) is strongly recommended when initiating single agent veliparib/placebo maintenance monotherapy.
- Anticancer Agents: Other anticancer agents are not permitted during the treatment portion of the study. All subjects will receive carboplatin + etoposide with veliparib/placebo at specified timepoints during the treatment portion of the study. The locally approved carboplatin and etoposide product labels or SmPCs should be referenced to determine if there are any contraindications associated with concomitant medications (e.g., phenytoin, etc.).
- Supportive Care: Best supportive care and treatment will be given as appropriate to each subject (antiemetics, antibiotics, transfusions, nutritional support, palliative treatment for pain, bisphosphonates or denosumab) according to institutional or clinical practice guidelines (e.g., ASCO, ESMO, or NCCN).
- Growth Factors: Biologic response modifiers administered for erythropoiesis (e.g., erythropoietin, darbepoetin alpha) and colony stimulating factors (e.g., neulasta, G-CSF, GM-CSF, etc.) may be administered according to institutional or clinical practice guidelines (e.g., ASCO, ESMO, or NCCN). Growth factors prophylaxis will not be allowed in Cycle 1 (Day -2 through Day 21) of the dose escalation cohorts. Growth factors prophylaxis is acceptable in Phase 2.

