### **5.5 Treatments**

#### **5.5.1 Treatments Administered**

Phase 1 subjects will receive the following:

- Designated doses of veliparib BID on Days –2 through 5 or Day –2 through 12 (14-day schedule) or Day –2 to 19 (continuous schedule) + Carboplatin AUC

5 mg/mL\*min administered on Day 1 and Etoposide 100 mg/m^2 administered on Days 1 through 3 of each 21-day cycle for up to 4 cycles.

- Exception: Phase 1 subjects receiving non-continuous veliparib will have their Cycle 2 dosing schedule altered as follows to allow for the evaluation of veliparib effect on etoposide exposure: veliparib BID on Days 2 through 5 or Days 2 through 12 + Carboplatin AUC 5 mg/mL\*min administered on Day 1 and Etoposide 100 mg/m^2 administered on Days 1 through 3 of a 21-day cycle.
- Phase 1 subjects with SD, PR or CR at the completion of all scheduled combination therapy cycles will receive veliparib (400 mg) monotherapy, BID continuously in 21-day cycles starting on Day 1 of each cycle starting at Cycle 5.

Phase 2 subjects will receive the following:

- Veliparib/Placebo 240 mg BID on Day -2 through 12 (14-day schedule) + Carboplatin AUC 5 mg/mL\*min administered on Day 1 and Etoposide 100 mg/m^2 administered on Days 1 through 3 of each 21-day cycle for up to 6 cycles.
- Phase 2 subjects with SD, PR or CR at the completion of combination therapy cycles will receive veliparib (400 mg) or placebo monotherapy, BID continuously in 21-day cycles starting on Maintenance Day 1 of each cycle.

The sequence of administration is as follows on days when veliparib is dosed in combination with chemotherapy as described in [Figure 3](#):

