## **11.0 Safety Analysis**

### **11.1 General considerations**

All safety analyses will be performed on Phase 2 AST population, and will be summarized by each treatment arm (A & B & C) for combination period alone. Safety analyses will include all data in the extracted database (no cutoff). For visit-wise safety analyses, the analysis visit widows as described in [Table 2](#) will be used to align data. There will be no statistical comparison for safety analysis unless otherwise specified.

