### **11.3 Deaths**

The number of subject deaths will be summarized 1) for deaths occurring within 30 days of the last dose of study drug in combination period, 2) for deaths that occurred more than

30 days of last dose of study drug in combination period, 3) for all deceased subjects. Death causes under each category will also be summarized.

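### The adverse-event window for the combination-period safety tables does not stop at the first maintenance dose, so for on-schedule entrants about 21 days of maintenance are counted as combination

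*SAP*

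**What the plan says.** SAP 11.1 sets the scope: safety data "will be summarized by each treatment arm (A & B & C) for combination period alone". SAP 11.2 sets the operative rule for adverse events, which is onset "prior to or on the 30 days of last dose of study drug in combination period". SAP 6.0 fixes the anchor as "the date of the last dose of veliparib/placebo or carboplatin/etoposide received during combination period", taking the later of the two. Starting maintenance neither moves that date nor closes the 30 days. SAP 11.4 uses the same anchor for laboratory data. The first of three death counts in SAP 11.3 is "for deaths occurring within 30 days of the last dose of study drug in combination period".

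SAP 9.0 treats the boundary differently. Its combination-period exposure calculations, and its counts of dose reductions, interruptions and delays, are restricted to data before maintenance.

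Protocol 5.5.1 gives combination dosing as "Veliparib/Placebo 240 mg BID on Day -2 through 12 (14-day schedule", within cycles of 21 days. The note to Protocol Table 6 says "Starting at Maintenance Day 1 veliparib will be dosed at 400 mg BID monotherapy continuous dosing for 21 days per cycle". Protocol 5.1 makes clear that this applies to Arm A and that Arms B and C take matching placebo.

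**The concern.** Arms A and B have the same planned combination regimen. A table confined to that period should show them differing only by chance. Under the 11.2 window, Arm A also collects events that begin after the switch to 400 mg BID, while Arm B collects events that begin on placebo. The A versus B contrast then contains a treatment difference that belongs to maintenance, and A versus C combines the effect of adding 240 mg BID to chemotherapy with the early effect of 400 mg BID alone.

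The first weeks of maintenance are a plausible time for new events. Protocol 5.2.3.2 says that antiemetic prophylaxis "is strongly recommended when initiating single agent veliparib/placebo maintenance monotherapy".

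There is also an internal mismatch. SAP 11.2 tabulates adverse events that led to reduction, interruption or delay of study drug. A reduction from the maintenance dose inside the 30 days could enter that table and be absent from the dose-modification summary in SAP 9.0, which stops earlier.

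**Working it through.** **Check of the plan's day count.** With no Day 0, Days -2 to 12 are 2 + 12 = 14 days, which reproduces the 14-day schedule. Days -2 to 19 are 2 + 19 = 21 days, which reproduces the cycle length. Day 1 of the next cycle is therefore Day 1 + 21 = Day 22.

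**Inputs.**
- Last combination dose, L: Day 12 of the last cycle on schedule (Protocol 5.5.1), or Day 3 if the last dose taken was etoposide.
- Window end: L + 30 (SAP 11.2).
- Maintenance start, M: Phase 2 gives no calendar day. Day 22 is an assumption, by analogy with Phase 1, where maintenance starts on Day 1 of Cycle 5 after four combination cycles. Protocol 5.3.1.1 allows 2 days either side for the first maintenance visit.

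**Formula.** Overlap = max(0, L + 30 - M + 1).

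| L | Window end | M | Overlap (days) |
|---|---|---|---|
| 12 | 42 | 22 | 42 - 22 + 1 = 21 |
| 12 | 42 | 20 | 23 |
| 12 | 42 | 24 | 19 |
| 3 | 33 | 22 | 33 - 22 + 1 = 12 |
| 12 | 42 | 43 | 0 |

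The last row is a start delayed by 21 days, the most that Protocol 5.7 permits for toxicity.

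**Share of the whole window, counted from Day -2 of Cycle 1.**
- Four cycles: last dose Day 3 × 21 + 12 = 75; window end Day 105; length 105 + 2 = 107 days; 21/107 = 20%.
- Six cycles: last dose Day 5 × 21 + 12 = 117; window end Day 147; length 149 days; 21/149 = 14%.

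SAP 4.2 can be read as giving the 400 mg BID continuous dosing to subjects in the two extra combination cycles, whereas Protocol 5.1 places it after the combination cycles. These passages must be reconciled, because they affect where the combination period ends.

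**How many subjects could be affected.** Take the planning values in SAP 4.3 and assume exponential PFS. The Arm A hazard is 0.63 × ln 2 / 5.5 = 0.0794 per month. The proportion progression-free is exp(-0.0794 × 2.76) = 0.80 at Day 84 and exp(-0.0794 × 4.14) = 0.72 at Day 126. Of 60 subjects, that is about 48 or 43, before any other reason for not entering maintenance.

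**After the change proposed under the fix.** For an on-schedule entrant the window ends on Day 21, which is 9 days after the Day 12 dose, and the overlap is 0. Subjects who never enter maintenance keep 30 days.

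**The case against.** The strongest reply is that the scope statement in SAP 11.1 already excludes the overlap, with 11.2 supplying a tail only for subjects who stop. SAP 6.0 gives the two periods separate dose dates, and the last sentence of 11.4 says the last dose depends on the analysis period. This shows that two programmers could build different tables. It does not supply the stop: 11.2 states a window without one, the sentence in 11.4 concerns laboratory data and sets no end at maintenance, and SAP 9.0 shows that the authors write the stop when they intend it.

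Four other points stand and limit the concern.
- Arms B and C both take placebo in maintenance, so B versus C gives a view of adding 240 mg BID that contains no maintenance veliparib. A reader might infer that every veliparib comparison in the safety tables is affected; that is not so.
- SAP 11.1 plans no statistical comparisons of safety data unless specified, and with about 60 subjects per arm Arms A and B will differ by chance anyway.
- A reader might infer that deaths are misclassified. The SAP 11.3 categories are labelled literally by time since the last combination dose, and the other categories capture later deaths and all deaths. Nothing is mislabelled or lost.
- A 30-day tail matches the Protocol's own convention (8.1.7.2). Shortening it only for maintenance entrants ties window length to progression and toxicity, which treatment may affect.

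**Conclusion.** The concern holds for adverse events, and for laboratory summaries on the same anchor. Followed as written, the plan puts maintenance-onset events into tables described as combination only. For on-schedule entrants the overlap is about 21 days (19 to 23 within the visit tolerance). It shortens with an earlier last combination dose or a delayed start, and vanishes if maintenance starts after Day 42. Holding maintenance for prophylactic cranial irradiation also reduces actual exposure in those days. Subjects who never enter maintenance are unaffected.

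A reader might go further and put a figure on the excess in Arm A, for example for nausea. The documents do not support one: they give no onset rates by phase for this regimen, and events starting in Arms B and C over the same days would have to be subtracted. The direction is plausible; the size of any bias is unknown. Efficacy is unaffected.

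**What to change.** In SAP 11.2, end the combination-period window at the earlier of 30 days after the last combination dose and the day before the first maintenance dose. Apply the same rule to the combination-period laboratory summaries in 11.4. Tabulate adverse events with onset on or after the first maintenance dose by arm in a separate maintenance table, so that none is dropped. Leave the 11.3 death categories as they are, or add a split by whether maintenance had started.

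No new data are needed. The cost is one date condition and one extra set of tables. There are two downsides: a delayed chemotherapy effect that first appears after maintenance starts is shown under maintenance, and the post-dose tail is shorter for maintenance entrants than for others. Keeping the present 30-day window as a sensitivity table addresses both.
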